### 17.3 Power Analyses:

This study is to be conducted for a period of three (3) years, starting from when the first subject is enrolled. As this is an open label safety study without a control group, no statistical analyses (other than descriptive) are proposed.

While a formal power analysis is not warranted, analysis of statistical power could be based on ASIA motor scores, whose variability has been most thoroughly detailed in the literature. This score ranges between 0 and 100. Data from a large-scale drug study on SCI showed that a 10-point change will reach a significance level of 0.05 if the number of patients with chronic cervical or thoracic injuries classified as ASIA A or B is  $\approx 8$  [51]. Recovery of sensory scores is typically more than 10%. Thus, the population size ( $n=12$ ) should therefore have sufficient power for many planned statistical tests, especially since participants will serve as their own controls.

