### 12.2 Expected Number of Participants

Twelve (12) participants with SCI for >1 year and show chronic persistent pain that has not fully responded to drug treatment.

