### 12.3 Treatment Groups

One (1) Treatment group. All participants will receive the same treatment (long-term DBS in PAG/PVG) and undergo the same procedural protocol. Ethical considerations forbid a control group that receives implant surgery without stimulation. Hence participants must serve as their own controls.

After internalization of the pulse generator (electronic stimulator) and subcutaneous tunneling of connecting cables to the electrode and 12-48 hours for recovery from this internalization procedure, stimulation will be applied to the patient. The patient will be asked to report their ongoing pain level, on a 0-10 numerical rating scale (NRS) with the stimulation turned off and, for each electrode contact, in small voltage steps up to the threshold for any aversive effects (if not seen in the first step). Floating, dizzy or warm feelings can be expected, based on literature reports. If there is no ongoing pain, cutaneous brushing to cause allodynia below the injury, at sensitive sites determined in the pre-surgical testing sessions, will be used. Blood pressure will also be measured by cuff before and during electrical stimulation. This will be repeated on week 12. The optimal level will be 67% of threshold for aversive or other unwanted effects (e.g. motor) or device maximum (10 V) if such effects are not observed. We expect the optimal voltage to be 4-10V. A frequency range of 10-20 Hz and pulse width range of 250-450  $\mu$ s is anticipated, but these parameters will be set according to the subject's responses. The subject returns home with the optimal stimulation settings after each programming session.

Subjects will receive monthly adjustment of stimulation levels to optimize analgesia on the NRS. They will be given the option of remaining in the study if any level becomes unpleasant in later months.

The subject will be given up to 4 different program groups after study week 16, differing in contacts, voltages, frequencies and pulse widths, all determined to be without adverse effect by the clinician programmer in the in-person office session. The subject is asked to switch program groups using their patient programmer. They switch immediately if relief is unsatisfactory, and stay with the best program for pain relief, or with any adequate program if the best is not determined, keeping a pain diary (score 0-10) at intervals of 24 hours or less to help determine the best program group.

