### 13.3 Inclusion Criteria

- a) Age: 22 - 60 years old at last birthday;
- b) Diagnosis of traumatic SCI at or above the 12th thoracic segment (T12) that occurred >365 days;
- c) Neuropathic pain below the level of injury, as determined based on pain in an area with neurological deficit and described as burning, shooting, electric, stinging etc.

- d) The injury must have occurred at least 1 year prior to entering the study and participants must have experienced chronic pain for a minimum of six months.
- e) The disability must have a grade on the American Spinal Injury Association Impairment Scale (AIS) of ASIA-A, ASIA-B, ASIA-C or ASIA-D as determined by qualified examiners.
- f) Pain (neuropathic) of moderate severity or greater is present, when the patient is taking their routine pain medication, with a score of at least 4 on a numerical rating scale (range of 0 to 10).
- g) Participants who are on medications for other conditions, such as diabetes, will be considered as candidates for this study. The dose will be monitored throughout the trial. (They will be excluded if the drug is being used to treat epilepsy, Parkinson's diseases, or other brain degenerative diseases.)
- h) Participants will be allowed to utilize over-the-counter drugs such as NSAIDs, acetaminophen and aspirin. Their use will be documented in the weekly pain assessments. A list of "allowed" medications will be provided to study participants. After the surgery, patients will be allowed to take stay on the protocol if they take Tramadol (50-100 mg, 2 times a day for up to 2 weeks) as a rescue drug in addition to their stable medication.
- i) The patient must be taking pain medication to maintain a stable level of medication from 4 weeks before surgery to 12 weeks after (the primary endpoint), except on the day of surgery. On the day of the surgery, in the presence of a physician who can provide immediate backup pain control if needed, medications will be stopped until the acute effects of DBS on analgesia have been evaluated.
- j) The participant must be willing to comply with the protocol including all scheduled visits.
- k) Autonomic dysreflexia can be present but is not a necessary requirement. Autonomic dysreflexia will be defined as rise of systolic pressure by more than 30 mm Hg during noxious skin stimulation or when the bladder or bowel are full, or apparently spontaneously over a period of minutes
- l) Literate at 8th grade level or above.

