In addition to the continual monitoring of adverse events, safety analyses will use generalized linear models. The main dependent variable of interest is the Numeric Rating Scale (NRS) score for pain. Additionally there will be a fairly large number of dependent variables derived from assessments of other symptoms. Distributions will be modeled as binomial (yes=1 or no=0) or multinomial (e.g., score =1, 2, or 0) or normal (e.g., heart rate peak power after tilt, quantitative sensory thresholds). Less frequently, a Poisson distribution will be appropriate (e.g., number of times the patient reports autonomic dysreflexia in a given period). An appropriate link function will be chosen for each assumed distribution. Covariates to be considered are injury level, injury completeness and electrode configuration. The hypotheses to be tested for any variable (using the above factor coding) is that  $B \succ A$ ,  $C \succ B$ ,  $D \succ B$  and  $D \succ C$ . Marginal means can be used for this (except in multinomial examples, when main effects must suffice). Some participants may lack data from one condition (if they immediately opted for continuous high-level stimulation after the initial untreated period). If the continuous treatment is stopped soon after it starts, only the placebo effect ( $A \succ B$ ) will be available. Representative independent variables from each type of symptom will be further explored by discriminant analysis, which can confirm that one or more treatment condition represents a distinct state in the multivariate outcome space.

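### Section 17.3 says 12 participants give sufficient power, but its only support is a significance level for ASIA motor score in ASIA A/B patients, which gives no power for that score or for NRS pain

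*Combined protocol and SAP*

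**What the plan says.** Section 17.3 first disclaims: only descriptive analyses are proposed, and a formal power analysis is called unwarranted. It then says that "analysis of statistical power could be based on ASIA motor scores", and cites a large drug study in spinal cord injury whose data "showed that a 10-point change will reach a significance level of 0.05" when the number of chronic cervical or thoracic ASIA A or B patients is about 8. It adds that sensory scores typically recover by more than 10%. From this it concludes that n=12 "should therefore have sufficient power for many planned statistical tests", the more so because participants are their own controls.

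Other sections bear on this:
- Section 17.1, in the text after Table 3: "The main dependent variable of interest is the Numeric Rating Scale (NRS) score for pain". The same paragraph plans generalized linear models and lists four directional hypotheses to be tested for any variable.
- Section 11.2: the core null hypothesis concerns neuropathic pain.
- Section 16: motor and sensory scores are one of four groups of trend-toward-efficacy parameters.
- Section 13.3 e): eligible grades are "AIS) of ASIA-A, ASIA-B, ASIA-C or ASIA-D as determined by qualified examiners".
- Sections 12.2 and 12.3: "Twelve (12) participants with SCI for >1 year", one treatment group. "Hence participants must serve as their own controls".
- Section 17.4: missing data are anticipated over the 52 weeks and will be imputed by regression. No rate is given.

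**The concern.** A statement that an effect of a given size reaches p = 0.05 with a given n is not a statement of power. If an observed 10-point change sits exactly on the significance boundary, a true 10-point change falls below that boundary about half the time. Section 17.3 moves from the one to the other without supplying what would connect them.

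The cited figure is also for a different outcome from the one the trial is mainly about, and for a subset of the patients it enrols. Nothing in it carries over to pain scores.

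What is at stake is how the results are read. The synopsis says the study is to help decide whether larger-scale work is warranted. An assurance of adequate power, if believed, would let a non-significant pain result be taken as evidence that stimulation does not help.

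**Working it through.** **Inputs from the documents.** n = 12, one arm, within-subject (12.2, 12.3). Cited result: 10 points, significance 0.05, n about 8, ASIA A or B (17.3). Power, SD, test, sidedness and the cited study's design are not given. For NRS pain, no SD of change is given anywhere.

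**The plan's own figure** cannot be reproduced, because those inputs are missing. What can be done is to solve for the SD under each plausible reading of the citation and carry it to n = 12.

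**Reading A: 10 points is just significant at n = 8, paired, two-sided.**
- Implied SD = 10 × √8 / t(0.975, 7 df) = 28.28 / 2.365 = 11.96. Standardised change = 10 / 11.96 = 0.836.
- Noncentral-t power for a true 10-point change: 53% at n = 8, 65% at n = 10, 75% at n = 12. Reaching 80% needs n = 14.
- Normal approximation: SD = 28.28 / 1.960 = 14.43. Power at n = 12 is Φ(10√12/14.43 − 1.960) = Φ(0.440) = 67%.

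**Reading A, one-sided.**
- Normal approximation: SD = 28.28 / 1.645 = 17.20. Power at n = 12 is Φ(10√12/17.20 − 1.645) = Φ(0.370) = 64%.
- By t, power at n = 12 is 70%.

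**Reading B: the cited comparison was between two groups of 8, just significant, two-sided.**
- SD = 10 / (t(0.975, 14 df) × √(2/8)) = 10 / (2.145 × 0.5) = 9.32.
- If that is taken as the SD of within-subject change in this one-arm trial, power is 92% at n = 12 and 85% at n = 10.

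**Reading C: n of about 8 was already sized for 80% power, paired, two-sided.**
- By t the standardised change is 1.156, so SD = 10 / 1.156 = 8.65. Power at n = 12 is 95% (93% by normal approximation).

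| Reading of the citation | Power at n = 12, true 10-point motor change |
|---|---|
| A, one-sided | 64% (normal), 70% (t) |
| A, two-sided | 67% (normal), 75% (t) |
| B, two-sided t | 92% |
| C, two-sided | 93% (normal), 95% (t) |

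**What can be said about NRS pain.** The SD of change is an assumption here, ranged from 1.5 to 3.0 points. The comparison is a simple paired baseline-to-follow-up t test, two-sided at 0.05.
- At n = 12, 80% power needs a standardised change of 0.889. In points this is 0.889 × SD.
- The 95% CI half-width is t(0.975, 11 df) × SD / √12 = 2.201 × SD / 3.464 = 0.635 × SD.
- Power for a given true change is from the noncentral t with noncentrality (change / SD) × √12.

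| Assumed SD | Change for 80% power | 95% CI half-width | Power, true change 1 point | Power, true change 2 points |
|---|---|---|---|---|
| 1.5 | 1.3 | 0.95 | 56% | 99% |
| 2.0 | 1.8 | 1.3 | 35% | 88% |
| 2.5 | 2.2 | 1.6 | 24% | 71% |
| 3.0 | 2.7 | 1.9 | 18% | 56% |

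With 10 completers (also an assumption) the 80% threshold is 1.00 SD, that is 1.5 to 3.0 points over the same SD range.

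**The case against.** The best defence is that this is a hedged aside and not a sample-size calculation. Section 17.3 disclaims a formal power analysis, section 17.2 labels the efficacy analysis descriptive, and section 17.1 calls the safety analyses mainly descriptive. The number 12 is not derived from the motor-score argument. This stands as far as it goes: no calculation is wrong, because none was made. It does not rescue the sentence. Section 17.3 still asserts sufficient power for planned statistical tests, and section 17.1 lists hypotheses to be tested. If tests are planned, the assurance is unsupported; if none are planned, it has no meaning.

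A second defence is that the cited source may already have built in power. The reference's title speaks of the statistical power needed for therapeutic trials, and the remark about own controls suggests that the cited comparison was between groups. This also stands, and it limits what can be concluded. A reader might infer from Reading A that sufficiency fails even for the motor score. The documents do not support that, since Readings B and C give 92% to 95%.

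Three other inferences should be resisted:
- That grade D participants sit near the 100-point ceiling, or that few participants will be grade A or B. The documents give neither baseline motor scores nor an expected mix. Grades A and B are eligible, so the cited population overlaps this one in part.
- That section 17.5 expects losses. It describes efforts to retain participants. Only section 17.4 anticipates missing data, and it gives no rate.
- That the NRS figures above describe the planned analysis. Section 17.1 plans generalized linear models, and Table 2 schedules 25 ISCI/NPSI pain assessments per participant. Modelling repeated scores could change the precision. The figures are illustrative only.

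**Conclusion.** The sentence in section 17.3 is wrong as written, because its conclusion does not follow from its premise. The cited fact is a significance level, not a power. It is compatible with about 64% to 95% power for the motor score at n = 12 over the readings worked here (75% under the literal two-sided paired t reading). It says nothing about NRS pain, for which power cannot be determined without an SD.

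A reader might go further and conclude that 12 participants are too few. The documents do not show that. Under the assumed SDs, power for a true 2-point pain change ranges from 56% to 99%, so 12 could suffice if the effect is large or the variability small. The defect is an unsupported assurance, not a demonstrated shortfall. It should be corrected because the plan should not claim a property it cannot show, particularly one that would colour the reading of a null pain result.

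**What to change.** In section 17.3, delete the motor-score argument and the sentence claiming sufficient power. Replace them with a short precision statement for NRS pain, marked as illustrative and with the SD of change labelled as an assumption, or sourced if the sponsor has data. For a simple paired baseline-to-follow-up comparison at two-sided 0.05 with 12 participants, 80% power needs a change of 0.89 SD (1.3 to 2.7 points for SD 1.5 to 3.0), and the 95% CI half-width is 0.95 to 1.9 points. With an assumed 10 completers, the threshold is 1.0 SD.

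Add that the study is not powered for the other outcomes, and that a non-significant result is not evidence of no effect.

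The cost is one paragraph and a less favourable statement than the present one. No extra patients, procedures or analyses are needed.

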### 17.4 Missing Data

Although every attempt will be made to avoid missing outcome data, missing data is anticipated with any longitudinal study. The missing data can be defined as intermittent or dropout. Although every effort will be made to prevent participants from missing visits or dropping out of this study, it is possible that some of the measurements planned over the 52 weeks will be missing. The impact of missing data will be examined by comparing means and standard deviations for participants that have and do not have the relevant missed visit data. The reason for missing data will be fully examined to confirm this assumption.

Missing data will be imputed using regression methods.

### 17.5 Participant Attrition

Because of the lengthy 44-week follow-up, efforts will be made to minimize the number of participants lost to follow-up by developing good rapport, making the participant feel comfortable with the research staff and having regular correspondence between assessments. To maintain contact and continued willingness for study participation at each visit participants will provide their current address and phone number, pager numbers, and e-mail address as well as contact information for at least two individuals who live outside of their household yet are likely to know their whereabouts. Contact information and contact history will be entered into an electronic database allowing regular review and update.

## 18 DIRECT ACCESS TO SOURCE DATA/DOCUMENTS

The Investigator agrees that qualified representatives of the Sponsor and regulatory agencies will have the right, both during and after this study, to conduct inspections and to audit and review medical records (CRFs, source data/documents, etc.) pertinent to the clinical study as permitted by the regulations. Patients will not be identified by name, and confidentiality of information in medical records will be preserved. The confidentiality of the patient will be maintained unless disclosure is required by regulations. Accordingly, the following statement (or similar statement) will be included in the informed consent document:

*Representatives of regulatory agencies, IRB/IECs, the Sponsor, and your personal physician may review your medical records and all information related to this study as permitted by law. Identifying information will not appear on any record received by the Sponsor. Your identity will remain confidential unless disclosure is required by law.*

## 19 QUALITY CONTROL AND QUALITY ASSURANCE

### 19.1 Quality Control and Assurance Checks

- a. Before enrolling any patients in this study, the Study Monitor and the Investigator will review the protocol, the CRFs and instructions for their completion, the procedure for obtaining informed consent, and the procedure for reporting AEs and SAEs.
- b. The Medical Monitor(s) will review the data for safety information; the Study Coordinator will review the data for legibility, completeness, and logical consistency.
- c. Additionally, the Study Coordinator will identify missing data, selected protocol violations, out-of-range data, and other data inconsistencies. Queries for data clarification or correction are forwarded to the investigator for resolution. A sample set of records will be fully audited against the corresponding CRFs.

### 19.2 Study Conduct

- a. This study will be conducted in accordance with the IRB/FDA-approved protocol, and applicable regulations constituting Good Clinical Practices.

### 19.3 Monitoring of the Study

Monitoring will be conducted by the University of Miami's Clinical Research Operations and Regulatory Support Quality Control (CRORS QC) office. Site visits are made before the study begins, at regular intervals during the study, and at the study closeout. Communication by telephone, mail and e-mail may be used as needed to supplement site visits. The Investigator and study personnel will cooperate with the Sponsor, provide all appropriate documentation, and be available to discuss the study. The purpose of the site visits is to verify the following:

- i. Adherence to the protocol. (The Investigator will not deviate from the protocol without prior written approval of Sponsor, except in emergencies. For medical emergencies, approval of a protocol deviation is not required, but Sponsor must be notified as soon as possible.)
- ii. The completeness and accuracy of the CRFs and the device dispensing and inventory record. (Adequate time and space for these visits shall be allocated by the Investigator.)
- iii. Compliance with regulations. The verification will require comparison of the source documents to the CRFs.

### 19.4 Protocol Deviations

Protocol deviations will be reported on the CRF, and will also be identified in data review by the Study Coordinator. Any deviation to the protocol that may have an effect on the safety or rights of the participant or the integrity of the study will be reported to the University of Miami Human Subject Research Office (UM HSRO) and FDA as soon as the deviation is identified.

All important deviations related to study inclusion or exclusion criteria, conduct of the trial, patient management or patient assessment will be documented and appropriately summarized.

### 19.5 Progress Reports

The PI will distribute bi-annual progress reports to the Funding Sponsor, the Miami Project to Cure Paralysis, communicating enrollment data, adverse events, and any outstanding issues or other relevant information. At the time of the IRB renewal the PI will submit in writing the frequency of the data monitoring, a summary of adverse events, other external factors or relevant information that might have an impact on the safety or ethics of the study, final conclusions regarding changes

to the anticipated risk/benefit ratio to study participation, and final recommendations related to the continuation, alteration, or termination of the study.

## 19.6 Audits and Inspections

The conduct of the study (including the selected CRFs and corresponding patient source records) will be periodically audited for compliance with FDA's Good clinical Practices and ICH-E6. Such audits will be conducted at least twice in the course of the Study, and will be conducted by the UM Office of Research Compliance & Quality Assurance (RCQA) auditors.

The knowledge of any pending compliance inspection/visit by the FDA, OHRP, or other government agency concerning clinical investigation or research, the issuance of Inspection Reports, FDA Form 483, warning letters or actions taken by any Regulatory Agencies including legal or medical actions and any instances of serious or continuing noncompliance with the regulations or requirements will be reported immediately to the Sponsor and the IRB.

## 20 ETHICS

### 20.1 Institutional Review Board (IRB)/Independent Ethics Committee (IEC)

The clinical protocol will be submitted to and approved by the University of Miami Human Subject Research Office (UM HSRO) and the FDA, and will not be initiated until written notification of approval of the research project is issued. Accurate and complete study records will be maintained and made available to representatives of the UM HSRO and FDA as a part of their responsibility to protect human subjects in research.

### 20.2 Informed Consent

- a. Participants with chronic spinal cord injury will be recruited from consecutive patients including men and women. Only participants who can provide their own Informed Consent without proxy will be included in the study. The discussions will take place in an area where privacy and confidentiality can be respected. The participant will be given sufficient time to comprehend the research and discuss the study before making a decision. The researcher will clearly explain the background/purpose, voluntary nature, commitment, risks, benefits, alternatives, and other elements, and will answer any questions. If the participant agrees to participate, written Informed Consent will be obtained and study intervention/treatment protocol will ensue.
- b. The device implantation surgery informed consent will be obtained 2-3 days prior to scheduling the procedure.
- c. It will be explained to the patient that they have the right to refuse to take part and/or withdraw from this study at any time without penalty or loss of care. Their ongoing medical care will not be affected by the decision to take part or not take part in this study. Participants who take part in the study will receive the same level of care that is considered the community standard. Patients who do not to take part in the study will also receive community standard care.

